## 7. Possible Discomforts and Risks:

Due to its antiplatelet properties,  $\omega$ -3 supplementation may increase the risk of bleeding at high doses when combined with antiplatelet/anticoagulant medications. Commonly reported side effects of  $\omega$ -3 supplements are usually mild and include unpleasant taste, bad breath, heartburn, nausea, gastrointestinal discomfort, diarrhea, headache, and odoriferous sweat.

The risks associated with the placebo, a mixture of vegetable oils, are similar to those for krill oil, and include upper respiratory tract infections, joint and back pain, gastrointestinal

disorders, and headaches. There is also a potential risk for worsening of cholesterol with the mixed vegetable oil placebo.

There are potential risks associated with the questionnaires, physical function tests, and cognitive tests administered in this study. Questionnaires and cognitive function tests pose a minimal risk of mental fatigue, embarrassment, discomfort, and/or frustration. Physical function tests have an inherent risk of physical discomfort, pain, and/or injury to the participants.

Blood draws carry minimal risks, including pain and/or discomfort, bruising and swelling, excessive bleeding, lightheadedness, and rarely, infection or nerve damage at the puncture site.

## 8. Possible Benefits:

*Benefit to participants:* Based on prior evidence, we believe that participants will directly benefit from krill oil supplementation in significant ways, including an improved blood profile of  $\omega$ -3 and  $\omega$ -6 fatty acids, downregulated inflammation, reduced pain, and improvements in physical function. Ultimately, these beneficial changes from krill oil will support their health and independence. Participants in the control group may also benefit from this study, as findings from the study may lead to advancements in therapies for chronic musculoskeletal pain. Furthermore, upon study completion, all participants will be able to obtain the information that has been collected throughout the study, including reports of their  $\omega$ -3 index,  $\omega$ -6: $\omega$ -3 ratio, inflammatory biomarkers, and dietary analysis. This information is not routinely assessed in clinical practice or easily obtained and will help inform the participants about their health. As such, we believe that the potential benefits to participants outweigh the relatively minor risks of the study.

*Public health benefits:* Results from this research have the potential to be widely beneficial to society, with important implications for public health and geriatric medicine. Chronic musculoskeletal pain contributes to loss of independence and quality of life, as well as shorter lifespan in older adults. Current approaches for pain management and functional decline in older adults have limited effectiveness and add to the increased risks of polypharmacy in this population. Non-pharmacological approaches, particularly nutritional interventions, are considered desirable candidates for primary or adjuvant treatment strategies to manage pain and maintain physical function in older adults with chronic musculoskeletal pain. This research will contribute to the understanding of the use of krill oil supplementation as a therapeutic approach for pain management and the maintenance of physical function in older adults with chronic musculoskeletal pain.

## 9. Conflict of Interest:

None.

Krill Oil for Pain and Physical Function in Older Adults

NCT06580912

03/05/2025

Statistical Analysis Plan

Feasibility and acceptability will be determined as (1) recruitment of at least 80% of the target sample ($n=32$), (2) attrition rate $\leq 20\%$, and (3) adherence rate $\geq 70\%$ (based on capsule counts and intake diaries). Changes in fatty acid profile (i.e., omega-3 index) will be analyzed using mixed-effects linear regression models with fixed effects for treatment group, time (as categorical), and a group-by-time interaction. While there is currently no guidance on what may constitute a minimal clinically meaningful change in plasma ω -3 index, current evidence supports that an ω -3 index $\geq 8\%$ may be protective against cardiovascular disease, whereas an index of $\leq 4\%$ indicates increased risk⁽⁸⁸⁾. Given the pilot nature of the trial, analyses will emphasize estimation of between-group differences and corresponding 95% confidence intervals rather than formal hypothesis testing. Estimates of variability and feasibility metrics will be used to inform outcome selection and design considerations for future trials. Changes in pain intensity, pain interference, and physical function will be analyzed using mixed-effects linear regression models, with fixed effects for treatment group, time (as categorical), and a group-by-time interaction, adjusting for age, sex, and BMI. A random intercept will be included for each participant, assuming an independent covariance structure. A 20% pain reduction on a 0-10 numeric rating scale is considered a clinically significant pain reduction.¹ A 1-point change in the SPPB and a 50-m increase in the 6MWT are considered clinically meaningful changes for older adults.² All analyses will follow an intent-to-treat approach, including all randomized participants in the groups to which they were assigned, regardless of adherence. A per-protocol analysis may also be conducted as a sensitivity analysis, including only participants with $\geq 70\%$ adherence. Missing data will be addressed using maximum likelihood estimation within the mixed-effects models, which accommodates data missing at random. Sensitivity analyses may be conducted using multiple imputation if warranted.

References

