**Table 1. Objectives and Endpoints**

| Objectives                             | Endpoints   | Justification for Endpoints  |
|--|---|--|
| Primary                         |   |  |
| Feasibility                            | 
 
• ≥80% recruitment
 
• <20% attrition
 
• ≥70% adherence
 
                                 | The pilot will serve as a small-scale study to inform the feasibility of future large-scale trials.                      |
| Secondary                       |   |  |
| Blood profile of essential fatty acids | 
 
• Omega-3 index ≥8%
 
• n-6:n-3 ratio ≥4:1
 
   | The purported physiological change of krill oil supplementation is an increased omega-3 index and reduced n-6:n-3 ratio. |
| Tertiary/Exploratory            |   |  |
| Pain and physical function             | 
 
• 20% pain reduction (0-10 scale)
 
• 1-pt improvement in SPPB
 
• 50-m improvement in 6MWT
 
 | Pain and physical function are the primary endpoints of a future fully powered clinical trial.                           |

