**6.5.I. Sample size and statistical approach:** This pilot study is designed as a small-scale test to guide the design and implementation of large-scale studies to evaluate the effectiveness of krill oil supplementation among older adults with chronic musculoskeletal pain. We will enroll 40 older adults who will be randomly assigned (1:1) to either krill oil ( $n=20$ ) or placebo ( $n=20$ ) for a 3-month trial duration. Approximately 16 participants per group after a 20% loss to follow-up is expected to provide sufficient data to indicate the feasibility of a larger study and to provide descriptive estimates of effects. **Aim 1.** Feasibility and acceptability will be determined as (1) meeting at least 80% of the recruitment goal ( $n=32$ ), (2) no more than 20% attrition, and (3) treatment acceptance and adherence ( $\geq 70\%$  consumption of prescribed doses and increased blood  $\omega$ -3 index). **Aim 2.** Mean changes in  $\omega$ -3 index and  $\omega$ -6: $\omega$ -3 ratio will be evaluated with paired-samples T-tests for within-group difference and independent-samples T-tests for between-group difference. An intention-to-treat approach will be used for between-group analyses. While there is currently no guidance on what may constitute a minimal clinically meaningful change in plasma  $\omega$ -3 index, current evidence supports that an  $\omega$ -3 index  $\geq 8\%$  may be protective against cardiovascular disease whereas an index of  $\leq 4\%$  indicates increased risk. Similarly, an  $\omega$ -6: $\omega$ -3 ratio of 4:1 or lower is considered optimal for health. Baseline and 3-month levels of the  $\omega$ -3 index and the  $\omega$ -6: $\omega$ -3 ratio will be compared against these benchmarks. **Aim 3.** Due to the repeated-measures design, we will use mixed-effects linear regression models to evaluate changes in pain intensity and functional interference (WOMAC), as well as changes in objective measures of physical function (SPPB, 6MWT). Fixed effects will be specified for the treatment group, time (in weeks), and a group\*time interaction effect. An independence covariance matrix structure will be assumed with a random intercept for each participant included. A 20% pain reduction on a 0-10 numeric rating scale is considered a clinically significant pain reduction. A 1-point change in the SPPB and a 50-m increase in the 6MWT are considered clinically meaningful changes for older adults.

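### The SAP gives no analysis or missing-data method for the n-6:n-3 ratio, a listed secondary endpoint; the only treatment comparison on record is the protocol's t-tests, which fit poorly with the SAP's intent-to-treat rule

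*SAP*

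**What the plan says.** Protocol Aim 2 defines the fatty acid profile as two markers, the omega-3 index and the n-6:n-3 ratio. Table 1 lists both as secondary endpoints and gives the expected effect of krill oil as an "increased omega-3 index and reduced n-6:n-3 ratio". Section 6.5.e obtains both from the same dried blood spot at baseline, week 6 and week 12.

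For both markers, protocol section 6.5.l (Aim 2) specifies "paired-samples T-tests for within-group difference and independent-samples T-tests for between-group difference", applied to mean changes. It adds: "An intention-to-treat approach will be used for between-group analyses". It also compares baseline and 3-month levels with benchmarks. It gives no rule for missing values.

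The SAP writes: "Changes in fatty acid profile (i.e., omega-3 index) will be analyzed using mixed-effects linear regression models", with fixed effects for group, categorical time and their interaction. The ratio appears nowhere in the SAP. Two general statements follow: "All analyses will follow an intent-to-treat approach, including all randomized participants in the groups to which they were assigned, regardless of adherence" and "Missing data will be addressed using maximum likelihood estimation within the mixed-effects models, which accommodates data missing at random". Imputation is optional: "Sensitivity analyses may be conducted using multiple imputation if warranted".

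**The concern.** A secondary endpoint with no analysis in the SAP leaves its method open to choice after the data are seen. The method that is on record also sits awkwardly with the rest of the plan, in three ways.

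- A t-test on change to week 12 needs a week-12 value. The SAP's missing-data method operates inside the mixed models and does not reach a t-test.
- Paired within-arm tests do not estimate the between-group difference that the SAP says it will emphasise. They invite the conclusion that one arm improved and the other did not, which is not a randomised comparison.
- Two markers calculated from one blood spot could be analysed by different methods on different sets of participants.

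**Working it through.** **The plan's own figures.** With 20 per arm and 20% loss, 20 × (1 − 0.20) = 16 per arm, as section 6.5.l states. The recruitment threshold is 0.80 × 40 = 32, also as stated. The documents give no SD, effect size, alpha or power for Aim 2, so there is no power calculation to reproduce.

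**What each document provides for the ratio.**

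| Item | Protocol 6.5.l | SAP |
|---|---|---|
| Treatment comparison | t-tests on mean change | none named |
| Benchmark | 4:1 or lower, descriptive | none |
| Missing data | no rule | likelihood, within mixed models only |
| Population | intention-to-treat for between-group analyses | all randomised, all analyses |

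The SAP keeps the protocol's benchmark statement for the index but drops the one for the ratio. The ratio is therefore absent from both the model and the benchmarks.

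**Participants omitted.** A baseline-to-week-12 change without imputation leaves out 40 × 0.20 = 8 of 40, and analyses 32. At 10% loss it leaves out 4, and at 30% loss 12.

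**Precision.** The 95% half-width for a difference in mean change, in units of the SD of change, is t(0.975, 2n − 2) × √(2/n):

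- n = 20 per arm: 0.64
- n = 16 per arm: 0.72

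**t-test on completers against a mixed model.** Assumptions: outcome SD 1 at each visit, true week-12 effect 1.0, 4 per arm missing week 12, baseline and week 6 observed for all, random-intercept data with known variance components, 2,000 runs per scenario. In the response-dependent scenario, krill-arm participants with a smaller week-6 response were more likely to be lost; placebo loss was random.

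| Within-person correlation | Random loss: SE, t-test / mixed | Reduction in SE | Response-dependent loss: mean, t-test / mixed |
|---|---|---|---|
| 0.5 | 0.351 / 0.338 | 3.7% | 1.12 / 1.00 |
| 0.7 | 0.271 / 0.265 | 2.2% | 1.09 / 1.01 |
| 0.8 | 0.225 / 0.219 | 2.7% | 1.07 / 1.01 |

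Both methods are unbiased under random loss. Under response-dependent loss the completer estimate is too large by about 0.07 to 0.12 outcome SD. A large-sample simulation (400,000 per arm, correlations 0.6, 0.6 and 0.75, 20% krill-arm dropout with log-odds slope 0.5 or 1.0 on week-6 change) gave 0.05 and 0.10, with the missing-at-random estimate on target.

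**Bias against interval width, in the same units.** The SD of change is √(2(1 − ρ)), which is 1.00, 0.77 and 0.63 for ρ = 0.5, 0.7 and 0.8. The half-width at 16 per arm is then 0.72, 0.56 and 0.46 outcome SD. The biases before rounding (0.121, 0.085 and 0.065) are about 17%, 15% and 14% of it.

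**Paired tests.** If both arms truly change by the same amount and each paired test has power p, exactly one is significant with probability 2p(1 − p). This is 0.32 at p = 0.2 or 0.8, and reaches its maximum of 0.50 at p = 0.5.

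**The case against.** The SAP sentence governs the fatty acid profile, which the protocol defines as both markers, so naming only the index may be loose drafting for a model meant to cover both. Alternatively, the SAP may focus on the index deliberately: section 6.5.e describes limitations of the ratio and says that the index may largely explain its associations. A reader might infer that the SAP assigns the ratio to the t-tests, or that the documents contradict each other on intention-to-treat. Neither is supported. The SAP is silent on the ratio, section 6.5.l names no time point for the t-tests, and neither document prescribes a completers-only analysis. The conflict arises only if week-12 samples are missing and nothing is imputed.

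Nor are the t-tests the only thing planned for the ratio. The benchmark comparison is also stated, and it bears directly on a Table 1 endpoint written as a threshold. It is not, however, a treatment comparison.

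The bias also needs dropout that tracks the week-6 response. Participants are blinded, and section 8 offers them their results only on completion, so they cannot react to the ratio itself. An indirect route through adherence or tolerability remains possible. The misuse of paired tests is partly contained, because section 6.5.l also specifies a between-group test and the SAP emphasises between-group estimates.

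These points limit the size of the problem and the certainty about intent. The gap remains under every reading: if the ratio was meant to be in the model, left on t-tests or dropped, the SAP should say so.

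**Conclusion.** The point holds as a gap in prespecification. A listed secondary endpoint has no analysis or missing-data method in the SAP, and the one treatment comparison on record would, without imputation, leave out about 8 of 40 randomised participants at the planned loss.

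A reader might infer serious bias or a large loss of precision; the figures do not support that. The mixed model's gain is about 2-4% in standard error under random loss, and removal of about 0.05-0.12 SD of bias if loss depends on week-6 response. Both rest on assumed correlations and dropout mechanisms, and on data that suit a random-intercept model. Someone missing both week 6 and week 12 would add only a baseline value, so the mixed model would recover less for such participants than these runs suggest.

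This is a secondary biomarker in a feasibility pilot, and the primary endpoints are unaffected. The change is still worth making, because it costs nothing and uses a method already planned for the other marker from the same sample.

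**What to change.** 1. In the SAP, extend the parenthesis after the fatty acid profile to name both the omega-3 index and the n-6:n-3 ratio.
2. Fit the same mixed model to the ratio, using baseline, week 6 and week 12 and all randomised participants. A log scale is reasonable for a ratio; state the choice in advance.
3. State in the SAP that this model replaces the Aim 2 t-tests in protocol section 6.5.l, and align that section.
4. Keep the benchmark comparison as descriptive. Its direction needs reconciling: Table 1 gives "n-6:n-3 ratio ≥4:1", whereas section 6.5.l treats 4:1 or lower as optimal.
5. Neither document states an analysis for the Aim 2 inflammatory biomarkers. If they are added at the same time, hs-CRP can use three visits, but IL-6 and TNF-α are measured only at baseline and week 12, so their model has two.

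The cost is one short edit to each document, with no new visits, samples or participants.

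### The SAP does not name its treatment contrast, and its mixed model uses the baseline outcome inefficiently; a common-baseline model would narrow the intervals without new data

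*SAP*

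**What the plan says.** **SAP, pain and function.** The outcome side is described this way: "Changes in pain intensity, pain interference, and physical function will be analyzed using mixed-effects linear regression models". No sentence says whether baseline is a response row or change scores are modelled. The terms listed on the other side are: "fixed effects for treatment group, time (as categorical), and a group-by-time interaction, adjusting for age, sex, and BMI". For the covariance the SAP then states: "A random intercept will be included for each participant, assuming an independent covariance structure". No baseline-outcome covariate, common-baseline constraint or covariate-by-time term is stated.

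**SAP, omega-3 index.** A mixed model with group, categorical time and their interaction. It lists no age, sex or BMI.

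**SAP, purpose and missing data.** On purpose, the SAP says that "analyses will emphasize estimation of between-group differences and corresponding 95% confidence intervals rather than formal hypothesis testing". On dropout, its position is: "Missing data will be addressed using maximum likelihood estimation within the mixed-effects models, which accommodates data missing at random". All randomised participants are to be included.

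**Protocol section 6.5.l.** Aim 2 compares mean changes in fatty acid measures using "independent-samples T-tests for between-group difference". Aim 3 uses a random-intercept model: "Fixed effects will be specified for the treatment group, time (in weeks), and a group\*time interaction effect". Neither adjusts for the baseline outcome, and neither includes age, sex or BMI.

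**Protocol Table 3.** A pre-treatment value of each outcome is already scheduled. The SPPB is taken at screening. WOMAC, 6MWT and the dried blood spot are taken at the baseline visit. All except the 6MWT are repeated at week 6, and all at week 12.

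**The concern.** The main output for these endpoints is a between-group estimate with its 95% CI, so the estimate and its precision are what the model has to deliver. Two things stand in the way.

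First, the contrast is not named. The interaction at week 12 and the group difference at week 12 (group plus interaction) are both between-group differences from the same fitted model. They have different variances and respond differently to the covariates. Nor does the SAP say whether baseline is a row of the response or change scores are the response.

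Second, randomisation makes the expected baseline means equal, but the model estimates a separate baseline mean for each arm. That discards information and leaves chance baseline imbalance in the estimate. The SAP also intends its variability estimates to inform future trials, and protocol Table 1 names pain and function as the primary endpoints of the next one, so the inefficiency could carry over into that design.

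**Working it through.** **Inputs.** From protocol section 6.5.l: 40 participants, 1:1, 20% loss. Assumed, because the documents give no figure: the baseline-to-follow-up correlation ρ, equal SDs at each visit (σ = 1), and, in the simulations, covariates explaining 20% of between-person variance.

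**The plan's own figure.** 20 × (1 − 0.20) = 16 per arm, or 32 in total. This reproduces. There is no SD, power or CI-width figure to check.

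**Why the covariates drop out of group-by-time.** Write the outcome as visit mean + group + group-by-visit + covariate terms + person intercept + error. Subtracting a person's baseline from their week-12 value removes every term that is constant over time, including age, sex and BMI. With complete data the interaction is the difference in mean change.

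**Precision under that contrast.**
- Difference in change: variance = 2(1 − ρ)σ² × 2/n.
- Baseline-adjusted: variance = (1 − ρ²)σ² × 2/n, multiplied by a small-sample factor 1 + 1/(2n − 4).
- Large-sample ratio: (1 + ρ)/2.

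Example, n = 16 and ρ = 0.5:
- Change: SE = √(2 × 0.5 × 2/16) = 0.354; × t(30) 2.042 = 0.722.
- Adjusted: SE = √(0.75 × 0.125 × 1.0357) = 0.312; × t(29) 2.045 = 0.637.
- Narrowing: 1 − 0.637/0.722 = 12%.

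| ρ (assumed) | Variance ratio (1+ρ)/2 | With small-sample factor | 95% half-width, change | 95% half-width, adjusted | Narrowing |
|---|---|---|---|---|---|
| 0.3 | 0.650 | 0.673 | 0.854 | 0.702 | 18% |
| 0.5 | 0.750 | 0.777 | 0.722 | 0.637 | 12% |
| 0.7 | 0.850 | 0.880 | 0.559 | 0.526 | 6% |
| 0.9 | 0.950 | 0.984 | 0.323 | 0.321 | 1% |

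Half-widths are in SD units with 16 per arm. With 20 per arm the narrowing is again 18%, 12%, 6% and 1%. At ρ = 0.5, 32 completers with adjustment are worth 32/0.777 ≈ 41 without it; at ρ = 0.9, 32.5.

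**Precision if the contrast is the week-12 group difference.** Before covariates its variance is σ² × 2/n, so the ratio for baseline adjustment is 1 − ρ²: 0.75, 0.51 and 0.19 at ρ = 0.5, 0.7 and 0.9. The gain is largest where the change-score gain is smallest.

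**Simulation.** 20 per arm, three visits, random intercept, REML, 300 datasets per setting.
- Adding age, sex and BMI, group-by-time, complete data: largest shift in the estimate 4 × 10⁻¹⁵, SE ratio 1.0000.
- Same, 20% dropout: mean shift 0.015 to 0.021 SD, maximum about 0.08 SD, SE ratio 0.999.
- Same covariates, week-12 difference: mean shift about 0.10 to 0.11 SD. At ρ = 0.5 the empirical SE went from 0.289 to 0.277 (complete) and from 0.346 to 0.319 (20% dropout).
- Change scores as the response: mean shift about 0.06 to 0.09 SD, with the empirical SE slightly larger.
- Model SE, SAP interaction versus common-baseline model: 0.315 to 0.272 (ρ = 0.5, complete), 0.344 to 0.306 (ρ = 0.5, 20% dropout), 0.244 to 0.225 (ρ = 0.7, complete), 0.266 to 0.249 (ρ = 0.7, 20% dropout).

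**Chance imbalance.** With 20 per arm, the baseline mean difference has SD √(2/20) = 0.32. A change-score estimate carries (1 − ρ) of it, so a typical imbalance shifts the estimate by 0.16 SD at ρ = 0.5.

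**Unequal SDs.** Suppose, as an assumption, that entry limits (SPPB 4–10, pain at least 4) halve the baseline variance. For pre-selection ρ = 0.5, the change variance is 0.75 + (1 − 0.5)² × 0.5 = 0.875 against 0.75 adjusted, and √(0.75/0.875) gives 7% narrowing. For ρ = 0.7, it is 0.51 + (0.3)² × 0.5 = 0.555 against 0.51, giving 4%. Without the small-sample factor, the equal-SD figures are 13% and 8%.

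**The case against.** The strongest defence is that the specified model is conventional and valid under randomisation. The primary objective is feasibility, pain and function are listed as exploratory, and the protocol itself says a pilot cannot adequately provide effect sizes. There is no power or CI-width target to miss. All of this stands, and it limits how much the point matters.

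Three stronger readings are tempting and should be resisted.
- A reader might infer that the SAP ignores the baseline outcome. If baseline is a response row and the effect is group-by-time, baseline is subtracted as the first repeated measure. It is used inefficiently, not ignored.
- A reader might infer that adjusting for age, sex and BMI cannot affect the treatment estimate. That is exact only for the interaction with complete data. It is nearly true with 20% dropout, and false if the effect is the week-12 difference or if change scores are the response. The SAP leaves this open. The covariates may also support the missing-at-random assumption, and the omega-3 index model lists none of them.
- A reader might infer a large, known loss of precision. The documents give no correlation or SD, and at ρ = 0.9 the change-score loss is about 1%.

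The open contrast does not rescue the text. Baseline adjustment reduces the variance under either the interaction or the week-12 difference, and leaving the choice to the analyst lets it alter the reported estimate.

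**Conclusion.** The point holds as a question of efficiency and specification, not of validity. The size rests on assumed correlations and equal SDs: CIs about 18% to 1% narrower for ρ from 0.3 to 0.9 under group-by-time, less if entry limits compress baseline spread, and more at high ρ if the effect is the unadjusted week-12 difference. Baseline adjustment would also take chance baseline imbalance out of the estimate. The affected endpoints are secondary (fatty acids) and exploratory (pain and function). No stated sample-size figure, power or feasibility threshold changes.

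**What to change.** In the SAP, for each continuous outcome including the omega-3 index:
- Name the week-12 between-group difference, with its 95% CI, as the estimate.
- Fit a constrained longitudinal mixed model by maximum likelihood. The baseline value is the first response row with one mean common to both arms, and the group effect enters only at the post-baseline visits.
- Keep all randomised participants and the week-6 data where collected. Keep age, sex and BMI as main effects where now specified.
- State that the screening SPPB, the only pre-treatment one in Table 3, is the SPPB baseline. Table 3 marks randomisation at screening, so also state that baseline-visit measures precede the first capsule; the common-mean constraint relies on this.

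Replace the Aim 2 between-group t-tests and the Aim 3 model in weeks in protocol section 6.5.l with the same model. An ANCOVA of week-12 values is a weaker alternative here: it drops participants without a week-12 value and ignores week 6, contrary to the SAP's all-randomised maximum-likelihood approach.

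The cost is a wording change in both documents. No new data are needed, and the model has one fixed effect fewer than the present one.

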| Weight  | X                    | X                       |                               | X                         |                             | X                        |
| Waist circumference   |                      | X                       |                               | X                         |                             | X                        |
| Physical Performance                                       |                      |                         |                               |                           |                             |                          |
| Short Physical Performance Battery (SPPB)                         | X                    |                         |                               | X                         |                             | X                        |
| Handgrip strength   |                      | X                       |                               |                           |                             | X                        |
| 6-minute walk test (6MWT)   |                      | X                       |                               |                           |                             | X                        |
| Whole blood collection                                     |                      | X                       |                               | X                         |                             | X                        |
| Dried blood spot (OmegaQuant)                                     |                      | X                       |                               | X                         |                             | X                        |
| CMP, CBC (safety), lipids, hs-CRP                                 |                      | X                       |                               | X                         |                             | X                        |
| Inflammatory markers (IL-6 and TNF- $\alpha$ )                    |                      | X                       |                               |                           |                             | X                        |
| Questionnaires   |                      |                         |                               |                           |                             |                          |

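### For pain and function outcomes measured at three visits, the planned random-intercept model imposes compound symmetry with no safeguard, so the 95% CI for week-12 change may be miscalibrated

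*SAP*

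**What the plan says.** The SAP models change in pain intensity, pain interference and physical function "with fixed effects for treatment group, time (as categorical), and a group-by-time interaction, adjusting for age, sex, and BMI". It then adds: "A random intercept will be included for each participant, assuming an independent covariance structure". Protocol section 6.5.l (Sample size and statistical approach, Aim 3) has the same structure: "An independence covariance matrix structure will be assumed with a random intercept for each participant included".

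On reporting, the SAP says that "analyses will emphasize estimation of between-group differences and corresponding 95% confidence intervals rather than formal hypothesis testing". On dropout it says: "Missing data will be addressed using maximum likelihood estimation within the mixed-effects models, which accommodates data missing at random". The only sensitivity analyses named are per-protocol and multiple imputation, both optional. Neither document mentions another covariance structure, robust standard errors or a degrees-of-freedom method.

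The schedule of activities (Protocol Table 3) sets how often each outcome is taken:
- WOMAC: baseline, week 6, week 12.
- SPPB: screening, week 6, week 12.
- GCPS-R: screening, baseline, week 6, week 12.
- 6MWT: baseline and week 12 only.

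The omega-3 index is also measured three times. The SAP gives it a mixed model too, but the covariance sentence follows the pain and function model, so no covariance is stated for the index.

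**The concern.** A single random intercept with independent residuals forces every visit to have the same variance and every pair of visits the same correlation. The word independent could refer to the random-effects matrix instead. With one random effect that says nothing, and default residuals still give compound symmetry.

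With three visits the model pools all within-person variation into one residual variance and applies it to the change from first measurement to week 12. If values 12 weeks apart are less alike than values 6 weeks apart, that pooled variance is too small for the longest contrast.

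At stake is the calibration of the 95% intervals that the SAP chooses to emphasize for its effect analyses. The variability estimates meant to inform later trials could also be affected, if they are taken from this model, which the SAP does not say. With complete data the between-group estimate itself is unaffected. With missing visits, the likelihood estimate also depends on the covariance matrix; that effect is not quantified here.

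**Working it through.** **The plan's own figure.** The Protocol states: "We will enroll 40 older adults who will be randomly assigned (1:1) to either krill oil" (n=20) or placebo (n=20), and: "Approximately 16 participants per group after a 20% loss to follow-up is expected to provide sufficient data". Check: 20 × (1 − 0.20) = 16 per group. It reproduces. The documents give no SD, correlation, power or CI width, so every covariance input below is an assumption.

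**Formulas.** Take complete, balanced data at times 0, 6 and 12 weeks, where 0 is the first measurement, with the SAP's categorical time and group-by-time term. The random-intercept fit then settles on the average variance v and average covariance c over the three visits.
- Variance of week-12 change used by the model: 2(v − c).
- True variance: s0² + s12² − 2·cov(0,12).
- SE ratio R = √(model / true). The sample size cancels.
- Large-sample coverage of a 95% CI = 2Φ(1.96R) − 1.

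**Example.** Equal SDs of 1 and correlations 0.7 (0–6), 0.7 (6–12), 0.49 (0–12): c = (0.7 + 0.7 + 0.49)/3 = 0.63. Model: 2(1 − 0.63) = 0.74. True: 2 − 2 × 0.49 = 1.02. R = √(0.74/1.02) = 0.85, coverage 90.5%.

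| Correlations 0–6 / 6–12 / 0–12 | SDs | Model | True | R | Coverage |
|---|---|---|---|---|---|
| 0.6 / 0.6 / 0.6 | 1, 1, 1 | 0.80 | 0.80 | 1.00 | 95.0% |
| 0.65 / 0.65 / 0.55 | 1, 1, 1 | 0.767 | 0.90 | 0.92 | 93.0% |
| 0.7 / 0.7 / 0.49 | 1, 1, 1 | 0.74 | 1.02 | 0.85 | 90.5% |
| 0.8 / 0.8 / 0.64 | 1, 1, 1 | 0.507 | 0.72 | 0.84 | 90.0% |
| 0.6 / 0.6 / 0.6 | 0.8, 1, 1 | 0.72 | 0.68 | 1.03 | 95.6% |
| 0.5 / 0.5 / 0.6 | 1, 1, 1 | 0.933 | 0.80 | 1.08 | 96.6% |

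In the three rows where correlation falls with time, R of 0.92, 0.85 and 0.84 means an SE about 8% to 16% too small. The model understates the variance of change by 15% (1 − 0.767/0.90), 27% (1 − 0.74/1.02) and 30% (1 − 0.507/0.72).

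**Small-sample check.** 20,000 simulated trials per scenario, 16 per arm, REML-type variance with t quantiles, covariates omitted. The comparator estimates the variance of week-12 change directly, which is what an unstructured matrix gives with complete data.

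| Scenario | Random-intercept coverage | CI width relative to comparator | Comparator coverage |
|---|---|---|---|
| 0.6 / 0.6 / 0.6 | 95.2% | 0.985 | 95.2% |
| 0.65 / 0.65 / 0.55 | 92.9% | 0.907 | 94.9% |
| 0.7 / 0.7 / 0.49 | 90.8% | 0.837 | 95.0% |
| 0.8 / 0.8 / 0.64 | 90.4% | 0.825 | 95.2% |

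If compound symmetry is true, freeing the matrix costs 1/0.985 = 1.015, or about 2% in width.

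**Two visits (6MWT).** Here v = (s0² + s12²)/2 and c = cov(0,12), so 2(v − c) = s0² + s12² − 2·cov(0,12), the true variance. R is 1 whatever the SDs. Simulated coverage was 94.9–95.1%.

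**Week-12 level instead of change.** The model uses v and the truth is s12². With equal SDs R is 1 whatever the correlations. With SDs 0.8, 1, 1.2 it is 0.84; with SDs 1.2, 1, 0.8 it is 1.27. The SAP speaks of changes, so the change contrast is the natural reading.

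**The case against.** The strongest reply is that the direction of error is assumed. Nothing in the documents gives an SD or a between-visit correlation. The table contains ratios below 1, equal to 1 and above 1, and only a 0–12 week correlation below the 6-week ones produces the marked narrowing. That stands. A reader might infer that the intervals are likely too narrow; the documents support only that they may be.

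Two features of the design might seem to settle the direction, and neither does.
- Entry limits on pain and SPPB could compress variance at the start. With equal correlations, that alone makes the change interval slightly too wide (1.03 with a first-visit SD of 0.8).
- The omega-3 index is expected to rise in the krill arm. That is a shift in means, which the group-by-time term already carries, and it does not by itself breach compound symmetry.

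Scope is the second reply. A reader might take these intervals to be the trial's main result. Feasibility is the primary objective, pain and physical function are listed as tertiary/exploratory in Protocol Table 1, and the SAP emphasizes estimation over testing. That also stands, and it limits the consequence.

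What the reply does not remove is that a restriction on the covariance is fixed in advance for three-visit outcomes, with nothing planned that would reveal or correct a failure.

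**Conclusion.** The point holds as a conditional one. For WOMAC and SPPB, and for GCPS-R, which has a fourth (screening) entry, the planned model gives a correct 95% CI for week-12 change only if compound symmetry holds or departures from it happen to cancel. For assumed correlations of 0.65–0.8 at 6 weeks and 0.49–0.64 at 12 weeks, with equal SDs, the SE is about 8–16% too small and coverage is about 90–93%. Under other assumed patterns the interval is correct or somewhat too wide.

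These sizes rest on complete data and unadjusted models, and on correlations that the documents do not supply. No feasibility result or sample-size figure changes. It is an inexpensive improvement to the exploratory effect analyses.

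**What to change.** In the SAP, and in Protocol section 6.5.l (Aim 3), for pain and function outcomes measured at three visits:
- Replace the random intercept with an unstructured covariance across visits, fitted by REML with Kenward-Roger degrees of freedom. This also settles the estimation and degrees-of-freedom method, where the SAP now says only maximum likelihood.
- State a fallback if the model does not converge: a simpler structure with small-sample-corrected robust standard errors.
- Say which GCPS-R assessments enter the model, since screening and baseline are both marked.
- State the covariance for the omega-3 index model in the same way. One matrix common to both arms is enough.

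The 6MWT change analysis needs no alteration on this account.

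The cost is wording only: six covariance parameters instead of two at three visits, and week-12 intervals about 2% wider if compound symmetry is true. If correlation falls with time they will be wider by more, because the planned ones would have been too narrow. No visits, data or participants are added.
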